9.4. Statistical Analyses

9.4.1. General Considerations

Statistical analysis of this study will be the responsibility of Lilly or its designee. Any change to the data analysis methods described in the protocol will require an amendment only if it changes a principal feature of the protocol. Any other change to the data analysis methods described in the protocol and the justification for making the change will be described in the CSR. Additional exploratory analyses of the data will be conducted as deemed appropriate.

All data will be entered, verified, and archived by a CRO external to Lilly and/or at Lilly. Data listings, summaries, and analyses will be performed by a CRO under the guidance and approval of statisticians at Lilly.

Summary statistics will be provided for the observed value, and change from baseline will be summarized.

Unless otherwise specified, listings will include all enrolled patients. Efficacy analyses will be conducted using the FAS.

Similarly, the exploratory measures (change in body weight from baseline and change in FBG from baseline) will be evaluated in the FAS population.

Also, safety analyses will be conducted on the safety population. The exploratory measures of vital signs (change in SBP, DBP, and pulse rate from baseline) will be analyzed using the safety population).

Unless otherwise specified, testing effect of dulaglutide on change from baseline will be conducted at a 2-sided alpha level of 0.05, and CIs will be calculated at 95%, 2-sided.

For continuous measures, summary statistics will include number of patients, mean, SD, median, minimum, maximum, and interquartile ranges for both the actual and the change from baseline measurements. Number of missing values will be specified along with this information.

For categorical measures, summary statistics will include sample size, frequency, and percentages. Number of missing values will be specified along with this information.

No multiplicity adjustment will be done in this study.

Change from baseline will only be calculated for patients with both baseline and post baseline values as:

$$\text{Change from baseline} = \text{postbaseline value} - \text{baseline value}.$$

The analysis for other continuous exploratory efficacy and safety measurements and continuous laboratory measures at 24 weeks will use the MMRM. It will be used to model change from baseline in FBG and any other safety or efficacy endpoints. Missing data will be assumed missing at random and will be accommodated by the MMRM.

The MMRM using restricted maximum likelihood will be done for analyses of change in FBG from baseline (note: statistical comparison will not be conducted) during the entire study period.

The MMRM could be repeated for other safety and efficacy endpoints.

For FBG, summary statistics will be provided for the observed value and change from baseline value based on the MMRM.

An unstructured covariance structure will be used to model the within-patient variability and implicitly adjust for missing data. If this analysis fails to converge, the following covariance structures will be tested in order.

1. Toeplitz with heterogeneity
2. Autoregressive with heterogeneity, by visit
3. Compound symmetry with heterogeneous variances, by visit
4. Toeplitz

5. Autoregressive
6. Compound symmetry without heterogeneous variances, by visit

The first covariance structure that converges will be used. The Kenward-Roger approximation will be used to estimate denominator degrees of freedom. Significance tests will be based on least-squares mean using Type III sum of squares.

If none of the models converge then an analysis of covariance using LOCF imputation with similar terms as in the MMRM (except no terms that include visit) will be used in its place.

The MMRM for each of the endpoints will include the respective baseline score and any covariate.

Baseline insulin use will be included as covariate in the model if convergence is met. Dose will be included as a covariate in the models, if appropriate. Details will be included in the SAP. Handling of missing, unused, and spurious data are addressed prospectively in the overall statistical methods described in the protocol and in the SAP, where appropriate. Adjustments to the planned analyses are described in the final CSR.

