9.4.5. Other Safety Analyses

Laboratory measurements

Continuous chemistry and hematology measures will be summarized by descriptive statistics at baseline and at different visits (Section 1.3) for the safety population.

Continuous chemistry and hematology measures will be summarized as change from baseline to Week 24 using the general linear model, with the baseline value of the response variable as covariate.

All laboratory measurement analyses will be repeated for the Per Protocol population.

AEs analyses

AEs will be listed by

- subject
- SOC
- Medical Dictionary for Regulatory Activities® PT
- severity, and
- relationship to the study disease, drug, or procedure for all subjects.

AEs (including injection-site reactions and neoplasms) will be summarized as TEAEs for the safety population. TEAEs are defined as events that are newly reported after the first study drug treatment or are reported to have worsened in severity after the first study drug treatment. The proportion of subjects experiencing each TEAE will be presented by PT, SOC, and treatment group. The proportion of subjects experiencing each TEAE that is assessed as possibly related to the study disease, drug, or procedures will also be summarized. TEAEs will be summarized by PT within SOC and by PT by decreasing frequency.

All SAEs will be listed by subject and summarized by treatment as counts and percentages. Similar analyses will be performed for discontinuations due to AEs.

All AEs analyses will be repeated for the PPS population.

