16.2 Analysis

Population: SAF and PP

Stratification: Table: Add the strata as needed in case subjects with dose modification exceeding 20% based on enrolled population as per section 7.3:

- a. Subjects on 1.5 mg only
- b. Subjects on 0.75 mg only
- c. Subjects with any dose modification*

* Subjects who have received at least one dose of 1.5 mg and at least one dose of 0.75 mg

Listing: by subject, visit and each laboratory test parameter

Statistics: Summaries of all the laboratory tests will include descriptive statistics of the following:

- Actual and change from baseline (number of patients, mean, SD, median, minimum, maximum, and interquartile ranges) (for quantitative measurements)
- Frequencies and percentages (n and %) (for qualitative measurements)

All the laboratory tests will be listed separately and listing of abnormal laboratory test will be presented.

Continuous chemistry and hematology measures will be summarized as change from baseline to Week 24 using the general linear model, with the baseline value of the response variable as covariate and the estimate and 95% CI will be presented. In addition, a descriptive analysis for actual value and change from baseline will be performed

using LOCF. It will be performed using the baseline or 12-week value, if the 24-week value is missing.

17. Vital signs

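### The protocol names two models for continuous laboratory measures; the SAP keeps only the Week 24 linear model, so the modelled mean shift may be modestly understated

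*Protocol*

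**What the plan says.** Protocol 9.4.1, in its general rules for continuous exploratory and safety measurements, says that "continuous laboratory measures at 24 weeks will use the MMRM". It adds: "Missing data will be assumed missing at random and will be accommodated by the MMRM".

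Protocol 9.4.5 sets a different model for laboratory data: "Continuous chemistry and hematology measures will be summarized as change from baseline to Week 24 using the general linear model". Baseline enters that model as the covariate. The section also plans a by-visit summary: "Continuous chemistry and hematology measures will be summarized by descriptive statistics at baseline and at different visits". Neither section says which model takes precedence.

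SAP 16.2 follows Protocol 9.4.5 and plans to summarise the "change from baseline to Week 24 using the general linear model". On adjustment and reporting, it specifies a model "with the baseline value of the response variable as covariate and the estimate and 95% CI will be presented". No MMRM appears in SAP Section 16. The same section adds a descriptive LOCF analysis of the actual value and the change ("It will be performed using the baseline or 12-week value, if the 24-week value is missing") and says that a "listing of abnormal laboratory test will be presented".

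SAP Section 5 declares that nothing in the planned analyses was changed. SAP 8.2 names LOCF for the HbA1c linear model and for the fallback analysis of covariance of weight, FBG, blood pressure and pulse. It gives no missing-data rule for the laboratory linear model.

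**The concern.** Two models are assigned to the same measurements, and one was dropped without being recorded as a change. The choice affects who contributes to the result. Hematology and clinical chemistry are sampled after baseline at Visit 5 (Week 12) and Visit 8 (Week 24). An MMRM uses both visits. A linear model for change to Week 24, with no imputation named, uses only patients with a Week 24 sample.

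The plan expects 20% dropout. If patients whose values have moved unfavourably by Week 12 are more likely to withdraw afterwards, the Week 24 model understates the mean shift. The MMRM would use their Week 12 values and correct for this under missing at random. The linear-model result is the only laboratory estimate for which SAP 16.2 plans a confidence interval. HbA1c, weight, FBG, blood pressure and pulse all receive an MMRM in the SAP, and no reason is given for treating laboratory data differently.

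**Working it through.** **Plan's own figures (Protocol 9.6).** 250 × (1 − 0.20) = 200 treated; 200 × (1 − 0.20) = 160 at the end of the study. Both reproduce. Up to 40 patients could therefore lack a Week 24 value.

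**Why the linear model uses Week 24 values only.** This is an inference from three places:
- SAP 7.5 computes change only when both the baseline and the post-baseline value exist.
- SAP 8.2 names LOCF for other models but not for this one.
- SAP 16.2 attaches LOCF only to an additional descriptive analysis.

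**Size of the bias.** Work in units of the SD of the Week 24 value given baseline. Let:
- m = share of patients with a Week 12 value who lack a Week 24 value;
- ρ = correlation between Weeks 12 and 24 given baseline;
- d = Week 12 difference, later leavers minus completers.

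Under missing at random given Week 12, later leavers would have averaged ρd away from completers at Week 24. The completer mean therefore misses the full mean by

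bias = m × ρ × d.

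The completer SE is 1/√160 = 0.079 SD. With b = bias/SE, the coverage of a nominal 95% interval is Φ(1.96 − b) − Φ(−1.96 − b). If data are missing completely at random, the ratio of the MMRM SE to the completer SE is √(1 − mρ²).

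The documents do not give dropout timing, ρ or d. I assume ρ from 0.3 to 0.7, d from 0.5 to 1.0, and that a quarter, half or all of the 40 have a Week 12 value. Earlier leavers are treated as random. This gives m = 10/170 = 0.059, 20/180 = 0.111 or 40/200 = 0.20.

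| Dropouts with a Week 12 value | Bias at ρ = 0.3, d = 0.5 | Bias at ρ = 0.7, d = 1.0 | Coverage | SE ratio (ρ 0.3 to 0.7) |
|---|---|---|---|---|
| 10 of 40 | 0.009 SD | 0.041 SD | 94.9% to 91.8% | 0.997 to 0.985 |
| 20 of 40 | 0.017 SD | 0.078 SD | 94.5% to 83.4% | 0.995 to 0.972 |
| 40 of 40 | 0.030 SD | 0.140 SD | 93.3% to 57.5% | 0.991 to 0.950 |

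For example, 0.20 × 0.7 × 1.0 = 0.14 SD and b = 0.14/0.079 = 1.77. At the other end, 0.059 × 0.3 × 0.5 = 0.009 SD and b = 0.11.

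**Simulation check.** In 4,000 trials of 200 patients, the true mean was 0, ρ was 0.5, and the log-odds of leaving after Week 12 rose by 1 per SD of the Week 12 value. The completer mean averaged −0.087 SD (sampling SD 0.078). The likelihood-based estimate averaged 0.001 SD (sampling SD 0.079). The correction removed the bias with essentially no loss of precision.

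**The case against.** A reader might infer that the plan throws away Week 12 laboratory data and can hide laboratory shifts. The documents do not support that.

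- SAP 16.2 carries the Week 12 value into a planned descriptive Week 24 summary, Protocol 9.4.5 asks for by-visit descriptives, and abnormal results are listed. Only the model estimate and its interval leave the Week 12 values out.
- Individual worsening is captured without a Week 24 sample. Protocol 8.2.4 has clinically relevant laboratory changes reported as AEs, 8.2.5 sets hepatic triggers, and 8.3.6 lists amylase and lipase elevations among events of special interest.
- Under Protocol 7.1, patients who stop dulaglutide stay in the study for the remaining visits. Only study withdrawal or a missed sample creates the gap.
- Apart from HbA1c and FBG, which have their own analyses, no laboratory measure is a study endpoint. These are other safety analyses in a single-arm study without hypotheses.
- In the per-protocol repeat, completing 24 weeks is an entry condition, so the issue largely disappears there.

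All of this stands, and it limits the point to one modelled mean. Nor do the documents call the linear model a complete-case analysis; the rule is simply unstated.

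Two further arguments carry less weight. The first is that the laboratory-specific section should override the general one. But 9.4.1 names laboratory measures outright, even though it later describes use of the MMRM for other endpoints as optional. Aligning 9.4.1 to 9.4.5 would also end the contradiction, but would leave the missing-data rule unstated. The second is that descriptive LOCF already covers the gap. It has no planned interval, and it assumes no change after the last value.

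**Conclusion.** The inconsistency is real: Protocol 9.4.1 conflicts with Protocol 9.4.5, and SAP 16.2 keeps one of the two models while SAP Section 5 declares no change. The consequence is small to moderate and confined to the modelled mean change in chemistry and hematology. Over the assumed ranges the bias runs from about 0.01 to 0.14 SD against an SE of 0.079 SD. It exceeds one SE only when most dropouts leave after Week 12 and clearly differ from completers by then. The direction is an understated shift if patients with worsening values leave, and the reverse if patients with improving values leave. Precision is not the issue, since the MMRM SE is at most 5% smaller. No percentage error can be given without assuming a true shift, which the documents do not supply. Severity is minor.

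**What to change.** Make Protocol 9.4.5 and SAP 16.2 agree with Protocol 9.4.1. Analyse chemistry and hematology measured at Weeks 12 and 24 with the already specified MMRM in the safety set, under its stated missing-at-random assumption. Keep the linear model for tests with a single post-baseline sample: the HDL/LDL/VLDL lipid panel, eGFR and the urinary albumin/creatinine ratio. An MMRM adds nothing there.

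If the sponsor prefers the linear model throughout, amend 9.4.1 to match, state the model's missing-data rule in SAP 16.2, and record the departure and its reason in SAP Section 5.

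The cost is SAP wording, a short protocol clarification and extra model runs. Protocol Appendix 2 lists about 30 analytes (34 if percent and absolute differential counts are both taken: 18 hematology and 16 chemistry). With two post-baseline visits the unstructured covariance has only three parameters, so the fallback sequence should rarely be needed. No new data are required.

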9.4.2. Primary Endpoints Analysis

AEs (deaths, SAEs, TEAEs, and hypoglycemia, including severe hypoglycemia)

Frequency and percentage of AE occurrence (including deaths, SAEs, TEAEs, hypoglycemia, including severe hypoglycemia and GI disorders) will be presented for the study duration using safety population.

The proportion of patients with AEs and SAEs occurring within the duration of the study (24 weeks) after being administered dulaglutide 1.5 or 0.75 mg will be presented.

The proportion of patients with AEs, TEAEs, and SAEs occurring within the duration of the study (24 weeks) after being administered dulaglutide 1.5 or 0.75 mg and 95% CIs will be estimated based on normal approximation.

The incidence of AE (death, SAE, and TEAE) will be summarized. The rate per year will be assessed using a negative binomial model with the log of the study treatment exposure time as an offset variable.

The incidence of hypoglycemic AEs will be summarized. The number of hypoglycemic events per subject over the study period will be analyzed as continuous variables and will be summarized (mean, median, SD, SE, minimum, and maximum).

The rate per year of hypoglycemic events, that is, the number of hypoglycemic events per patient-year (365.25 days) will be assessed using a negative binomial model, with baseline HbA1c and baseline insulin usage as covariates and the log of the study treatment exposure time as an offset variable.

The incidence of AEs will be calculated based on the number of new AEs out of the total eligible population using the following formula:

$$\text{Number of new AEs post intervention/Total eligible population *100.}$$

Exposure-adjusted AE incidence will be presented by the severity and preferred term for the primary analysis.

It is defined as

Number of patients with new or worsened AEs during treatment period

Patient-year exposure/365.25

Patient-year exposure is counted in days up to the AE (or end of time at risk for subjects without AE).

Incidence of gastrointestinal AEs

The incidence of GI AEs per week will be plotted over time from baseline up to 24 weeks. The proportion of subjects with at least 1 GI AE will be plotted from baseline up to Week 24. A plot of prevalence by severity (mild, moderate, or severe) for nausea, vomiting, and diarrhea over the 24-week period will be provided for the rate of GI AEs.

Three Cox proportional hazard models, each with covariates for baseline HbA1c and baseline insulin use, will be used to model the time to the first onset of nausea, vomiting, or diarrhea TEAE, respectively.

9.4.3. Secondary Endpoints Analysis

Change in HbA1c from baseline to 24 weeks of therapy with dulaglutide 1.5 or 0.75 mg

The change in HbA1c level from baseline to Weeks 12 and 24 for all available data including post-rescue medication values will be analyzed using descriptive statistics (mean, median, SD, SE, minimum, maximum, and number with missing values). In addition, for the actual value and change from baseline, a descriptive analysis using LOCF will be performed, using the baseline or 12-week value, if the 24-week value is missing or occurred after use of rescue medication.

For subjects requiring rescue medication (see Section 6.1.1), HbA1c values recorded after the first administration of rescue medication will not be considered for analysis, and these values will be considered as missing. The MMRM, as described in Section 9.4.1 will be used for analysis of the change in HbA1c level from baseline to Weeks 12 and 24.

If convergence is not met in the MMRM, the change in HbA1c level from baseline to Week 24 will be analyzed using the general linear model for the FAS population. The general linear model will evaluate the change from baseline in HbA1c level as the dependent variable and the baseline value of HbA1c as covariate. The LOCF method of missing value imputation will be used.

FAS population will be used for analysis as per planned treatment.

The analyses will be repeated for the per-protocol population.

9.4.4. Exploratory Endpoints Analysis

The actual values and change from baseline will be summarized by descriptive statistics (mean, median, SD, SE, minimum, and maximum) by visit for the FAS population and for the per-protocol population for the following parameters:

- body weight
- FBG

- SBP
- DBP, and
- pulse rate.

Details of exploratory analyses will be documented in SAP.

9.4.5. Other Safety Analyses

Laboratory measurements

Continuous chemistry and hematology measures will be summarized by descriptive statistics at baseline and at different visits (Section 1.3) for the safety population.

Continuous chemistry and hematology measures will be summarized as change from baseline to Week 24 using the general linear model, with the baseline value of the response variable as covariate.

All laboratory measurement analyses will be repeated for the Per Protocol population.

AEs analyses

AEs will be listed by

- subject
- SOC
- Medical Dictionary for Regulatory Activities® PT
- severity, and
- relationship to the study disease, drug, or procedure for all subjects.

AEs (including injection-site reactions and neoplasms) will be summarized as TEAEs for the safety population. TEAEs are defined as events that are newly reported after the first study drug treatment or are reported to have worsened in severity after the first study drug treatment. The proportion of subjects experiencing each TEAE will be presented by PT, SOC, and treatment group. The proportion of subjects experiencing each TEAE that is assessed as possibly related to the study disease, drug, or procedures will also be summarized. TEAEs will be summarized by PT within SOC and by PT by decreasing frequency.

All SAEs will be listed by subject and summarized by treatment as counts and percentages. Similar analyses will be performed for discontinuations due to AEs.

All AEs analyses will be repeated for the PPS population.

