7.1.3. Temporary Discontinuation

Criteria for temporary discontinuation of dulaglutide

The investigator may temporarily interrupt study treatment due to an AE, clinically significant variation in laboratory value, COVID-19 infection, hospital visits, travel, emergency surgery, hospitalization, or shortage of study treatment supply. Interruption in study treatment for 4 weeks or more will lead to permanent discontinuation of study treatment.

This will be allowed once at any time during the study. This information should be documented by the investigator. The study drug discontinuation decision will be taken post the titration in the initial 4-6 weeks of the study.

Guidance for temporary discontinuation of dulaglutide

Every effort should be made by the investigator to maintain participants in the study and to restart dulaglutide promptly, as soon as it is safe to do so.

Participants will continue their study visits and follow-up according to the SoA.

Participants should resume the dose prescribed before the temporary dosing interruption or as advised by the investigator.

Recording temporary discontinuation of dulaglutide

The dates of dulaglutide interruption and restart must be documented in source documents and entered in the CRF.

Participant noncompliance should not be recorded as interruption of dulaglutide in the CRF.

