9.3. Analyses Sets

For purposes of analysis, the following populations are defined:

Participant Analysis Set	Description
Enrolled	
 All participants who sign informed consent form and are screen positive
FAS	
 All patients who received at least 1 dose of study treatment and have at least 1 measurement of HbA1c after study treatment
Per-protocol set	
All patients in the FAS who meet the following criteria
 
 have no important protocol deviations that could impact the assessment of the primary objective (see SAP) are at least 80% compliant with the study drug in terms of dose taken have no instance of deviation from persistence with study drug in terms of no more than the 15 days gap between 2 consecutive doses complete the treatment phase (24 weeks) for the primary endpoint
Safety analysis set	
 All patients who received at least 1 dose of study treatment

Abbreviations: FAS = full analysis set; HbA1c = hemoglobin A1c; SAP = statistical analysis plan.

The FAS is used to analyze endpoints related to the efficacy objectives, and the safety analysis set is used to analyze the endpoints and assessments related to safety.

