6.3 Per-Protocol Analysis Set (PP)

All patients in the FAS who meet the following criteria

- Have no important (major) protocol deviations that could impact the assessment of the primary objective
- are at least 80% compliant with the study drug in terms of dose taken
- have no instance of deviation from persistence with study drug in terms of no more than the 15 days gap between 2 consecutive doses
- complete the treatment phase (24 weeks) for the primary endpoint

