15.2 Analysis

An overview summary will be presented for TEAEs and SAEs as (n=number of subjects, m=number of events and %=percentage of subjects) by treatment i.e., Dulaglutide, using SAF population.

The listings of Pre-treatment AEs, TEAEs, Serious AEs and AEs resulting in death and AEs leading to study discontinuation will be presented, using SAF population, by treatment group and subject number. AEs will be listed by subject, SOC, Medical Dictionary for Regulatory Activities® PT, severity, outcome, and relationship to the study drug, or procedure for all subjects.

Note: If there are uncoded adverse events, then the uncoded category will be added in the AEs by SOC/PT summary tables.

15.2.1 Incidence of TEAEs, Drug-related TEAE, Serious adverse events (SAEs) and AEs leading to death

Population: SAF and PP

Stratification: Table: Add the strata as needed in case subjects with dose modification exceeding 20% based on enrolled population as per section 7.3:

- a. Subjects on 1.5 mg only by Primary SOC and PT in decreasing order
- b. Subjects on 0.75 mg only by Primary SOC and PT in decreasing order
- c. Subjects with any dose modification* by Primary SOC and PT in decreasing order

* Subjects who have received at least one dose of 1.5 mg and at least one dose of 0.75 mg

Statistics: Treatment emergent AEs, Drug-related TEAE, Serious adverse events (SAEs) and AEs leading to death will be summarized as (n=number of subjects, m=number of events and %=percentage of subjects) for table.

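### AE analyses are repeated in a per-protocol set whose members must complete 24 weeks of treatment, so deaths before Week 24 (and, on the plain reading, stops for AEs) cannot appear there

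*Protocol*

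**What the plan says.** Protocol 9.4.5 describes the summaries of TEAEs and SAEs, adds that "Similar analyses will be performed for discontinuations due to AEs", and closes with "All AEs analyses will be repeated for the PPS population".

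The SAP implements the repeat as follows:

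- **15.2.1**, on the safety and per-protocol sets: "Treatment emergent AEs, Drug-related TEAE, Serious adverse events (SAEs) and AEs leading to death will be summarized".
- **15.2.2**, severity tables for TEAEs and SAEs, on the same two sets.
- **18.1.2, 18.2.2 and 18.3.2**, the three primary AE endpoints, on the full analysis set (FAS) and the per-protocol set.

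Protocol 9.3 and SAP 6.3 define the per-protocol set in the same way. A member must belong to the FAS ("All patients who received at least 1 dose of study treatment and have at least 1 measurement of HbA1c after study treatment"), have no important protocol deviation, and meet three treatment conditions:

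- The completion rule asks that the patient "complete the treatment phase (24 weeks) for the primary endpoint".
- The persistence rule, as worded in SAP 6.3, asks that patients "have no instance of deviation from persistence with study drug in terms of no more than the 15 days gap between 2 consecutive doses".
- The compliance rule, as worded in Protocol 9.3, asks that patients "are at least 80% compliant with the study drug in terms of dose taken".

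Protocol 7.1.3 adds that "The investigator may temporarily interrupt study treatment due to an AE, clinically significant variation in laboratory value", among other reasons, and makes the stop permanent once the interruption reaches 4 weeks.

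**The concern.** The per-protocol set is chosen by looking at what happened after the first dose, and what happened includes the outcome being counted. A patient who dies before Week 24 has not completed treatment and is removed, and so is a patient who stops dulaglutide early because of an AE. The set is then used to tabulate deaths and tolerability.

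A supportive analysis is useful when it could disagree with the main one for a reason worth knowing. For deaths before Week 24 this one returns zero whatever the true rate. The study exists to document safety in Indian patients for a marketing authorization clause (Protocol 2.1), and neither document warns that the per-protocol AE tables are conditional on finishing treatment. A reader who sees a zero there may take it as information about the drug.

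**Working it through.** **Planned numbers (Protocol 9.6).** Screened 250, screen failure 20%: 250 × 0.80 = 200 treated. Dropout 20%: 200 × 0.80 = 160 at study end. Both stated figures reproduce. About 200 − 160 = 40 treated patients fall outside the per-protocol set if dropout means not completing treatment. The compliance, gap and deviation rules can only reduce the set further, so 160 is roughly its maximum.

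**Deaths.** A patient who dies before Week 24 cannot complete a 24-week treatment phase. The per-protocol count is 0 for any true rate. One such death is 1/200 = 0.5% in the safety set and 0/160 in the per-protocol set (exact 95% upper limit 1 − 0.025^(1/160) = 2.28%). Deaths in the Week 24 to 28 follow-up can still appear.

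**Permanent stops for an AE.** On the plain reading, someone who stops the drug early has not completed the treatment phase, and the count is again 0. Protocol 7.1, however, keeps such patients in the study for the remaining visits, so completion could be read as attending Week 24. The 80% rule then still applies. With 24 planned weekly doses (an assumption; the documents do not give the count), 0.80 × 24 = 19.2, so at least 20 doses are needed. Only a stop after about dose 20 could enter.

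**Temporary interruptions.** One missed weekly dose leaves 2 × 7 = 14 days between doses, inside the 15-day limit. Two missed doses leave 3 × 7 = 21 days, outside it. A patient who interrupts for an AE as 7.1.3 allows and misses two doses is excluded because of that AE.

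**Illustration for AE stops.** The documents do not split dropout by reason, so the counts are assumptions. The safety-set figure is x/200, with Clopper-Pearson limits for two cases. The last column uses the plain reading.

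| Assumed AE stops among 40 dropouts | Safety set | Per-protocol set (at most about 160) |
|---|---|---|
| 6 | 3.0% (1.1% to 6.4%) | 0 |
| 12 | 6.0% (3.1% to 10.2%) | 0 |
| 20 | 10.0% | 0 |
| 40 | 20.0% | 0 |

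**Crude proportion with any AE.** Let p be the proportion in completers, x the AE-driven dropouts (each with an AE) and q the proportion in the other dropouts. The safety set gives (160p + x + (40 − x)q)/200; a per-protocol set of all 160 completers gives p.

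- q = p = 50%, x = 20: (80 + 20 + 10)/200 = 55.0% against 50.0%. The per-protocol figure is 5 points low.
- p = 70%, q = 42%, x = 5: (112 + 5 + 14.7)/200 = 65.85% against 70.0%. The per-protocol figure is 4.15 points high.

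The sign changes at x = 40(p − q)/(1 − q). With q = 0.6p this is 5.9, 11.4 and 19.3 of the 40 dropouts for p = 30%, 50% and 70%. The direction therefore depends on inputs that the documents do not give.

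**Exposure-adjusted first-AE incidence.** Assume p = 30% or 50%, a constant hazard, the same hazard in dropouts for other reasons (followed to Week 12), and AE-driven dropouts having their AE at Week 4 or 12. The per-protocol rate is then 7% to 26% below the safety-set rate for x = 10 to 20, and equal to it at x = 0.

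**The case against.** The strongest reply is that the per-protocol tables are a repeat and not the safety result. Protocol 9.3 and 9.4.2 assign safety to the safety set, and SAP 15.2.1 and 15.2.2 tabulate it there as well. The SAP's AE overview and its listings of deaths and AE discontinuations use the safety set only. Withdrawal reasons, including AE and death, are tabulated on the enrolled set (SAP 10). The excluded events therefore remain visible. This stands, and it limits the weight of the point. It does not give the repeat a purpose. It is also weaker for SAP section 18, where the per-protocol tables of the primary AE endpoints stand beside FAS tables and no safety-set table is named.

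Three stronger readings are tempting, and the documents do not support them:

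- **All AE rates in the set are biased low.** That is the expected direction when AEs drive dropout. For the crude any-AE proportion it is not guaranteed, as the second worked case shows.
- **The set must show fewer severe GI events.** Protocol 6.5 allows a patient with GI AEs to have the dose reduced and later reintroduced. Such a patient can finish and stay in the set.
- **The SAP itself specifies a per-protocol table of AE stops.** It does not. That table follows only from the protocol's general sentence. The structural zero in the SAP's own tables is AEs leading to death, for deaths before Week 24.

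A further fair point is that laboratory change at Week 24 in adherent patients is a legitimate supportive question. This point does not argue for removing it.

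**Conclusion.** The point holds in a limited form. Deaths before Week 24 are zero in the per-protocol set by construction. Permanent stops for an AE are zero on the plain reading of the completion rule; on the looser reading only late stops, after about dose 20 of an assumed 24, could enter. Two missed weekly doses during a permitted AE interruption also exclude a patient. The remaining AE rates describe people who tolerated treatment and should not be read as rates for treated patients.

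The size depends on how many of the roughly 40 expected dropouts are AE-driven, which the documents do not state: 6 to 12 stops would be 3.0% to 6.0% of treated patients, against none on the plain reading. A reader might infer that the trial's main safety result is compromised. The documents do not support that through this route, because tables on the safety set are untouched. The use of the FAS for the primary AE endpoints in SAP section 18 is a separate matter, and this point stands even if the safety set is restored there. The repeat should be dropped because it cannot inform on deaths or early intolerance and could be mistaken for doing so.

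**What to change.** Remove the per-protocol repeat from the AE, SAE, death and GI analyses: the closing sentence of Protocol 9.4.5, the per-protocol half of SAP 15.2.1 and 15.2.2, and the per-protocol half of SAP 18.1.2, 18.2.2 and 18.3.2. Report these analyses on the safety set. If a supportive look is wanted, split safety-set events at the last dose into on treatment and after stopping.

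Keep the per-protocol set for HbA1c, FBG and body weight. The per-protocol laboratory analyses (Protocol 9.4.5, SAP 16.2) may stay if labelled as conditional on completing treatment. State in SAP 6.3 whether completing the treatment phase means staying on drug to Week 24 or attending the Week 24 visit.

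The cost is protocol and SAP wording. There are fewer tables to produce, and the sponsor gives up a supportive table set.
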